8.4.2 Swedish national registries

Sweden has a well-developed population-wide register system with longitudinal follow-up data. The persons are identified in the registers with a unique personal identification number (PID) and thus the records can be linked for research purposes on subject level between the registers. Permissions to use the data may be received upon providing a research plan to the authorities responsible for the registers. The protocol is also subjected to relevant Ethical Committee's review and approval. The data permit processes and timelines for data permit granting by the authorities responsible for the registers vary between different registers and countries, as well as the requirements for the local research collaboration and the publication of results [[R15-4861](#)].

The nationwide prescription register contains information on outpatient medication purchases in pharmacies. All prescribed medicines purchased in community pharmacies are included irrespective of reimbursement status.

Based on the feasibility assessment, the Sweden national registers met the minimal data requirements ([Table 5](#)). The following data sources will be used to construct the Sweden cohort by linkage: The National Patient Register, the Swedish Prescribed Drug Register, the Swedish Cancer Register, the Causes of Death Register, the National Diabetes Register, and the Longitudinal integration database for health insurance and labour market studies.

To determine renal impairment, eGFR values will be extracted from the National Diabetes Register. Information on important covariates such as number of albuminuria tests and blood pressure measurements will also be extracted from the National Diabetes Register. Further, proxies of socioeconomic position will be obtained from the Longitudinal integration database for health insurance and labour market studies.

The study data will be extracted from the relevant registers using the following general process. First, patients in the study cohort with the unique PID number are identified from the prescription register. A unique dummy study identification number (SID) is created for each PID by the prescription register holder. The list with the PID-SID pairs will be provided from the prescription register holders to the other register holders. Each register holder extracts the relevant data according to the study protocol and links the data to the PID-SID list.

Subsequently, the register holders decode the data by destroying the key between the PID and SID permanently and provides the de-identified study data to the applicant. Thus, only de-identified data will be provided for performing the analysis of the study data. In Sweden, the full study data including follow-up period until the end of 2020 will be available during in March 2022.

8.4.3 Finnish data sources

An additional, feasible data source in Europe includes the national registers in Finland, which were evaluated in the feasibility assessment before this study.

As in Sweden, Finland has a well-developed population-wide register system with longitudinal follow-up data. The persons are identified in the registers with a unique PID and thus the records can be linked for research purposes on subject level between the registers. Further, the data obtained from registers can be linked with data obtained from the EMR databases.

The following Finnish nationwide data sources will be included: Care register for health care (HILMO), Register of primary health care visits (AvoHILMO), Special reimbursement register, Prescription register, Cause of death register, Cancer register, Population register centre, and Statistics Finland ([Table 5](#)). HILMO and AvoHILMO include diagnoses associated with healthcare encounters in specialized and primary care, respectively. The Special reimbursement register will be used for identification of chronic comorbidities. This register includes patients who are entitled for special refunds of medicine expenses based on their chronic conditions. The Finnish nationwide Prescription register contains information on outpatient medication purchases in pharmacies. The register contains information on all purchased prescribed medicines within the reimbursement scheme. Cause of death register includes time of death and the cause of death classified according to the ICD categorization. Cancer register includes information on all diagnosed cancers, details of the tumour, and description of treatment.

The study data will be extracted from these registers using the general process as described above for Sweden ([Section 8.4.2](#)). Information about highest level of education will be obtained as a proxy for socioeconomic status from Statistics Finland, and information on patient's place of residence and migration will be obtained from Population register centre.

Further, to obtain data on important potential confounders, specifically BMI, blood pressure, smoking, and laboratory measures such as HbA1c and eGFR, EMR databases will also be included in the study. Four regional EMR databases (Helsinki, Espoo, Vantaa, and Helsinki University Hospital [HUS] area), covering both primary and secondary care in the capital area of Finland, will be contacted separately to obtain access to their data. The data obtained from different data sources will be linked as described previously ([Section 8.4.2](#)).

Permissions to use the data may be received upon providing a research plan to the authorities responsible for the registers. The protocol is also subjected to relevant Ethical Committee's review and approval. The data permit processes and timelines for data permit granting by the authorities responsible for the registers vary between different registers and countries, as well as the requirements for the local research collaboration and the publication of results [[R15-4861](#)].

In Finland, all the data will be delivered to and analysed in the remote access server environment provided by the national permit authority Findata. The data holders will extract the relevant data and deliver it to Findata for pseudonymization. Before data delivery to the

Findata server environment, the data holders will collect and manage data according to their own standards. After the data is delivered to the Findata server environment by the data holders, [REDACTED] will process the data.

[REDACTED] will use the study identification numbers for data linkage on individual level. [REDACTED] will have access to pseudonymized raw data without PINs. Therefore, the researchers at [REDACTED] will have access to data where individuals cannot be directly identified.

In Finland, the full study data including follow-up period until the end of 2020 will be available in June 2022.

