8.3.3 Covariates

Variables potentially associated with urinary tract cancers, such as socio-demographic variables including age, sex, socioeconomic status, body mass index, smoking and alcohol consumption, laboratory measurements, concomitant medications, comorbidities, and duration of look-back period (see [Section 6.1](#)), will be identified for study participants as recorded prior to the index date (see [Annex 6](#) for list of covariates to be included in the study). With the exception of exposure to toxic chemicals such as arsenic, known risk factors for urinary tract cancers are captured in CPRD and the national registers from Sweden and Finland.

Study participants will also be classified by indicator variables on the calendar time of cohort entry (by quarter) whether the index treatment (empagliflozin, or DPP-4 inhibitor) was added to existing medication (adding on), or if the index treatment was initiated as a replacement for another antihyperglycemic medication (switching to empagliflozin, or DPP 4 inhibitor), and whether this treatment was received as monotherapy or as dual or triple combination therapy. A variable indicating whether or not patients were receiving insulin at the index date will also be created.

The confounding due to covariates in this section are to be accounted for at minimum by design or analysis when estimating the risk of urinary tract cancers with the defined

The examples of covariates in Table 4 describe the comorbidities, treatment history, and socio-demographic variables that will be considered for inclusion. These variables along with times of occurrence/diagnosis of comorbidities, times of prescription/dispensing of drugs and times of recording of the socio-demographic variables in combination with the exposure and outcome variables define the minimal required dataset.

Table 4

Baseline covariates to be considered for inclusion alternatively or simultaneously in primary, secondary, and further analyses

Covariate	Exact matching	PS matching	Stratification	
Database variable (for CPRD only) ¹				
Patient database (Aurum vs GOLD)	Yes	Yes		
Socio-demographic variables				
Age	Yes	Yes	Yes	
Sex	Yes	Yes	Yes	
Socioeconomic status (if available)		Yes		
Calendar year of index date		Yes		
Duration of look-back period		Yes		
Insulin concomitant (or cumulative duration of) use		Yes	Yes	
Other oral antihyperglycemic medication use		Yes		
Comorbidities				

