8.4 DATA SOURCES

Prior to the development of the protocol for this study, a feasibility assessment of three databases in Europe (CPRD [GOLD and Aurum] and data with potential for linkage [HES (Outpatient and Admitted Patient Care), and ONS mortality statistics] in the UK and the national registers in Sweden and Finland) was performed with the aim to detail the minimum data requirements for the study and to assess, for each potential data source, the data quality, completeness of recorded information for urinary tract malignancies, and possibility of linkage with cancer registries, mortality registries and other data sources. The minimal data requirements for data sources which were assessed are listed in [Table 5](#).

Table 5

Minimum data requirements and data availability for the UK and the national registries in Sweden and Finland.

	The UK				Sweden					Finland						
	CPRD (GOLD and Aurum)	HES	Mortal ity		Patient	Prescri ption	Cancer	Cause of	Diabet es	HILM O	AvohI LMO	Special Reimb	Prescip tions	Cause of	Cancer s	EMR databa
Age	X	X	X	X	X	X	X	X	X	X	X	-	X	X	X	
Sex	X	X	X	X	X	X	X	X	X	X	X	-	X	X	X	
Medication	X	-		X ³	X	-	-	X ⁵	-	-	-	-	X	-	X	
DDD	X	-	-	X	X	-	-	-	-	-	-	-	X	-	-	
Purchase date	X ¹	-	-	X	X	-	-	-	-	-	-	-	X	-	-	
Diagnoses	X	X	-	X ⁴	-	X	-	X	X	X	X ⁷	X ⁹	-	X	-	
Date of diagnosis	X	X	-	X	-	X	-	-	X	X	X ⁸	-	-	X	-	
Time of death	-	-	X	-	-	X	X	-	-	-	-	-	-	X	X	
Cause of death	-	-	X	-	-	X	X	-	-	-	-	-	-	X	X	
Smoking	X	-	-	-	-	-	-	X	X ⁶	X ⁶	-	-	-	-	X	
BMI	X	-	-	-	-	-	-	X	X ⁶	X ⁶	-	-	-	-	X	
HbA1c	X	-	-	-	-	-	-	X	-	-	-	-	-	-	X	

X = available in the register, - = not available in the register

1 Prescription date; 2 Month and year; 3 Treatment given in hospitals (no full coverage); 4 No primary care data; 5 Only type of medication; 6 Partial availability based on applicable diagnosis codes; 7 Only chronic diseases included in the special reimbursement scheme; 8 Start and end dates of the special reimbursement; 9 In case a special reimbursement was included in the purchase

AvoHILMO=Register of primary health care visits, BMI=body mass index, CPRD=Clinical Practice Research Datalink, DDD=Defined daily dose, EMR=electronic medical record, HbA1c=Glycated haemoglobin A1c, HES=Hospital Episode Statistics (Outpatient data, and Admitted Patient Care data), HILMO=Care register for health care; UK =The United Kingdom

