Estimated glomerular filtration rate (eGFR) at index date	
eGFR estimate derived from serum creatinine measurement using the CKD-Epi equation:
 $\text{eGFR (mL/min/1.73 m}^2\text{)} = 141 \times \min(\text{S}_{\text{cr}}/\text{K}, 1)^a \times \max(\text{S}_{\text{cr}}/\text{K}, 1)^{-1.209} \times 0.993^{\text{Age}} \times 1.018 \text{ [if female].}$ 
a = -0.329 (females) or -0.411 (males).
 
Evaluated at index using closest value to index date.
	
Time-fixed Continuous Categorical <15 (ml/min/1.73 m²) (kidney failure) 15-29 (ml/min/1.73 m²) (severely decreased) 30-44 (ml/min/1.73 m²) (Moderately to severely decreased) 45-59 (ml/min/1.73 m²) (Mildly to moderately decreased) 60-89 (ml/min/1.73 m²) (Mildly decreased) ≥90 (ml/min/1.73 m²) (Normal)
	
UK: CPRD Sweden: NDR Finland: EMR databases

Proprietary confidential information © 2024 Boehringer Ingelheim International GmbH or one or more of its affiliated companies

Renal impairment at index date	
The variable is evaluated at index date and indicates an eGFR < 60 (ml/min/1.73 m²) in all available history prior to index date.
 
Evaluated at index date using all available history prior to index date.
	
Time-fixed Categorical Yes No
	
UK: CPRD Sweden: NDR Finland: EMR databases

UTI or pyelonephritis	
The variable is initialized at index date and indicates a register record with a diagnosis of UTI or pyelonephritis using all available history. If no diagnosis prior to index date, it is time-updated to indicate any diagnosis of UTI or pyelonephritis after index date.
 
ICD-10 and READ diagnosis codes for UTI or pyelonephritis in Annex I.
 
Initialized at index and updating from index date onwards.
	
Time-dependent Categorical: Yes No
	
UK: CPRD Sweden: NPR Finland: HILMO, AvoHILMO

Liver disease at index date	
The variable is evaluated at index date and indicates a register record with a diagnosis of liver disease using all available history prior to index date.
 
ICD-10 and READ diagnosis codes for liver disease in Annex I.
 
Evaluated at index date using all available history prior to index date.
	
Time-fixed Categorical: Yes No
	
UK: CPRD Sweden: NPR Finland: HILMO, AvoHILMO

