ICU admission at index date	
The variable is evaluated at index date and indicates a record of ICU admission in all available history prior to index date.
 
Evaluated at index date using all available history prior to index date.
	
Time-fixed Categorical: Yes No
	
UK: CPRD Sweden: NA Finland: HILMO, AvoHILMO

Pancreatitis at index date	
The variable is evaluated at index date and indicates a register record with a diagnosis of pancreatitis using all available history prior to index date.
 
ICD-10 and READ diagnosis codes for pancreatitis in Annex I.
 
Evaluated at index date using all available history prior to index date.
	
Time-fixed Categorical: Yes No
	
UK: CPRD Sweden: NPR Finland: HILMO, AvoHILMO

Proprietary confidential information © 2024 Boehringer Ingelheim International GmbH or one or more of its affiliated companies

Congestive heart failure at index date	The variable is evaluated at index date and indicates a register record with a diagnosis of congestive heart failure using all available history prior to index date. ICD-10 and READ diagnosis codes for congestive heart failure in Annex I.	Time-fixed Categorical: Yes No	UK: CPRD Sweden: NPR Finland: HILMO, AvoHILMO
Evaluated at index date using all available history prior to index date.			
Systolic blood pressure at index date	Systolic blood pressure measurement value in mm Hg at index date. Evaluated at index using closest value to index date.	Time-fixed Continuous Categorical ¹ : < 120 ≥120-<139 ≥140-<159 ≥160	UK: CPRD Sweden: NDR Finland: EMR databases
Evaluated at index using closest value to index date.			
Diastolic blood pressure at index date	Diastolic blood pressure measurement value in mm Hg at index date. Evaluated at index using closest value to index date.	Time-fixed Continuous Categorical ² : < 80 ≥80-89 ≥90-99 100 or higher	UK: CPRD Sweden: NDR Finland: EMR databases
Evaluated at index date using all available history prior to index date.			
Hypertension at index date	The variable is evaluated at index date and indicates a register record with a diagnosis of hypertension, or two records within 6 months (180 days) of systolic blood pressure ≥ 140 and diastolic blood pressure ≥ 90 using all available history prior to index date. ICD-10 and READ diagnosis codes for hypertension in Annex I.	Time-fixed Categorical: ² Yes No	UK: CPRD Sweden: NPR, NDR Finland: HILMO, AvoHILMO, EMR databases

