9. MISSING DATA

A high frequency of missing values is not expected for most variables, with the possible exception of lifestyle and biological measurement variables. For the medical history conditions / comorbidities to be collected for inclusion in the propensity score, the absence of a code for a condition will be interpreted as an absence of the event.

If a variable is missing for only some of the patients, a missing data category will be added and utilized in the analysis. If a variable is missing for more than 50% of patients, removal of the variable from the relevant model or analysis (propensity score, multivariable Cox's regression, NCC matching) will be considered.

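### The SAP leaves the Finnish special reimbursement register out of its comorbidity definitions, although the protocol names it for that purpose and the data are already held

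*Protocol*

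**What the plan says.** **Finland, protocol.** Section 8.4.3 assigns the register a task: "The Special reimbursement register will be used for identification of chronic comorbidities". It sits alongside two encounter registers: "HILMO and AvoHILMO include diagnoses associated with healthcare encounters in specialized and primary care, respectively". The footnotes to Table 5 say that the reimbursement register covers only chronic diseases within the scheme, and that it carries start and end dates of the entitlement.

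**Finland, SAP.** Table 1 lists the reimbursement register from 1996, HILMO from 1996 and AvoHILMO from 2011. In Tables 12 and 13 the sources for diagnosis-based covariates such as stroke, myocardial infarction, autoimmune disease and COPD read "UK: CPRD Sweden: NPR Finland: HILMO, AvoHILMO". For hypertension the entry is "Finland: HILMO, AvoHILMO, EMR databases". The reimbursement register appears only in the algorithms that identify type 2 diabetes, exclude other diabetes and censor on it (section 4.2.4 and Table 4).

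**Missing codes.** SAP section 9 states that "the absence of a code for a condition will be interpreted as an absence of the event". Protocol 8.7.1.7 has the same rule.

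**Sweden.** SAP Table 13 takes urinary tract infection or pyelonephritis from the National Patient Register (NPR) alone. Protocol Table 5 footnotes that register "4 No primary care data". Protocol 8.3.3 nevertheless says, toxic chemicals excepted, that "known risk factors for urinary tract cancers are captured in CPRD and the national registers from Sweden and Finland".

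**The concern.** The two documents disagree on where Finnish chronic comorbidities come from, and the SAP's list of changes (section 3) does not record the switch. The omission meets the missing-code rule in an unhelpful way. Someone who holds an entitlement for a chronic disease, but has no matching code in HILMO or AvoHILMO, is entered as not having it.

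The planned checks cannot show this. Matching, the 10% standardised-difference criterion and the choice of base-model covariates all work on recorded status. A condition recorded for only some of the patients who have it can look balanced while part of the true imbalance remains. COPD is a fair example. It is a marker of smoking, and smoking in Finland is only partly available from diagnosis codes and otherwise comes from regional EMR data covering about 26.7% (protocol 8.9.2).

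**Working it through.** **1. Sources side by side (Finland).**

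| Use | Protocol | SAP |
|---|---|---|
| Chronic comorbidities | Reimbursement register named, besides HILMO and AvoHILMO (8.4.3) | HILMO and AvoHILMO; EMR added for hypertension (Tables 12, 13) |
| Diabetes type | Special reimbursement with a diagnosis (8.2.5) | Reimbursement register (4.2.4, Table 4) |
| Time since first diabetes diagnosis | Source not specified | HILMO and AvoHILMO (Table 12) |

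The last row is inconsistent within the SAP. Section 4.2.4 looks for type 2 diabetes in the reimbursement register first and turns to AvoHILMO only if nothing is found. A patient included through the register can therefore have a late first-diagnosis date, or none, in a propensity-score candidate.

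**2. Who is affected.** Table 6 of the protocol plans 18,269 Finnish empagliflozin initiators of 67,490: 18,269/67,490 = 0.271, about 27%. None were indexed in 2014 and 91 in 2015, so (18,269 − 91)/18,269 = 99.5% were indexed in 2016 or later, at least five years after AvoHILMO began.

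**3. Scale, by illustration only.** The documents give no recording shares, covariate prevalences or confounder effects. Assume perfect specificity and the same sensitivity s in both groups. Let pE and pD be the true prevalences on empagliflozin and DPP-4 inhibitors, and RR the confounder's rate ratio. After exact balance on recorded status, the true prevalence among matched comparators is

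P0 = pE·s + (1 − pE·s)·pD(1 − s)/(1 − pD·s),

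and the hazard ratio is multiplied by [1 + (RR − 1)pE]/[1 + (RR − 1)P0].

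Take pE = 0.10, pD = 0.20, RR = 2.
- s = 0.5: P0 = 0.05 + 0.95 × 0.10/0.90 = 0.156; factor 1.10/1.156 = 0.952.
- s = 0.7: factor 0.969.
- s = 0.9: P0 = 0.09 + 0.91 × 0.02/0.82 = 0.112; factor 1.10/1.112 = 0.989.
- No adjustment: 1.10/1.20 = 0.917.

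With RR from 1.5 to 3 the factor runs from 0.974 to 0.915 at s = 0.5, and from 0.994 to 0.980 at s = 0.9. Swapping the prevalences (pE = 0.20, pD = 0.10, RR = 2, s = 0.5) gives P0 = 0.10 + 0.90 × 0.05/0.95 = 0.147 and a factor of 1.20/1.147 = 1.046, so the sign turns round.

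What the omission costs is the difference between two values of s. If the register raised s from 0.7 to 0.9, the Finnish factor would move from 0.969 to 0.989.

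**4. In the pooled estimate.** Use the inputs under protocol Table 8 for renal cancer, a null effect and no between-country variance. The weight is 1/(1/E1 + 1/E0), where E1 and E0 are expected events.
- UK: E1 = 16,360 × 2.4 × 26.5/100,000 = 10.4, E0 = 31.2, weight 7.8.
- Sweden: E1 = E0 = 32,334 × 2.2 × 58.0/100,000 = 41.3, weight 20.6.
- Finland: E1 = 18,269 × 2.4 × 71.6/100,000 = 31.4, E0 = 62.8, weight 20.9.

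Finland's share is 20.9/49.3 = 0.42. A Finnish factor of 0.969 becomes 0.969^0.42 = 0.987 in the pool, and 0.989 becomes 0.995. Table 9 puts the minimum detectable hazard ratio for renal cancer at 1.62.

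**The case against.** The best reply is that little is lost. AvoHILMO still supplies primary-care diagnoses, and nearly all Finnish index dates fall well after it began. The register covers only conditions in the scheme, and the documents do not say which Table 13 conditions those are or how many entitled patients lack a coded visit. Dispensed antihypertensives and diuretics, lipid drugs and oral steroids are separate propensity-score candidates, as is the duration of treated diabetes from prescriptions held since 1994. Matching is within country, so both groups share the same sources. Protocol 8.9 and 8.9.1 concede limited risk-factor data and possible residual confounding. Some SAP sensitivity sections and the Finnish and Swedish code lists cannot be seen.

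Most of this stands, and it limits the size of the problem. It does not explain why a source that the protocol names, and the SAP holds, is unused for the stated purpose. A general limitation on missing data does not cover data in hand. COPD has no comparable medication covariate.

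Three stronger readings are tempting. A reader might infer that the SAP also narrowed the Swedish sources. It did not: protocol 8.4.2 names no Swedish primary-care register. Nor is the missing-code rule a SAP departure, since the protocol has it too. A reader might add Finland and Sweden together, giving (18,269 + 32,334)/67,490 = 75% of initiators. These are separate matters, touching about 27% and 48%. Finally, a reader might conclude that the bias hides harm. That needs an assumed direction of channelling, and step 3 shows that the sign reverses with it.

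**Conclusion.** The Finnish point holds: the SAP departs from protocol 8.4.3 without recording it, and the missing-code rule turns entitlement-only patients into patients without the condition. The handling of time since first diabetes diagnosis is a second instance of the same gap. The consequence is confined to Finland and to conditions in the scheme. It is probably small: under the assumed inputs a few percent on the Finnish hazard ratio, and about 1% on the pooled renal estimate. Those figures show scale only; the documents support neither a size nor a direction.

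The Swedish gap is real but is a limitation that both documents share. Protocol 6.1 lists chronic bladder irritation and infections among the risk factors, so the 8.3.3 statement is too broad where infections managed in primary care leave no code in the NPR.

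**What to change.** 1. In SAP Tables 12 and 13, add the Finnish reimbursement register as a source for each chronic condition that the scheme covers, with an entitlement starting before index counted as 'Yes'. Add it also to time since first diabetes diagnosis, with the entitlement start as a candidate first-diagnosis date. If the omission was intended, record and justify it in SAP section 3.
2. In protocol 8.3.3, qualify the sentence on captured risk factors: in Sweden, urinary infections managed only in primary care are not recorded in the source used.
3. Optionally, run a Swedish sensitivity analysis that supplements the NPR code with dispensings of antibiotics specific to urinary infection. This gains sensitivity but loses specificity and makes the definition differ between countries, so it should not replace the main definition.

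The cost of item 1 is a mapping of scheme categories to the SAP conditions and some reprogramming; the register is already in the planned extract. Item 2 is wording. Item 3 needs a drug list that the documents do not contain.
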